##### ***Small/Medium ( $\leq 12$ mm) Wide-Necked IAs***

IAs measuring  $\leq 12$  mm in size comprise approximately 80% of all intracranial aneurysms. The risk of rupture for IAs less than  $< 10$  mm in size is approximately 1.0% per year and the risk of rupture increases with aneurysm size. As ruptures can lead to SAH, a devastating complication with a case-fatality rate of over 50%, these small and medium wide-necked aneurysms are commonly treated endovascularly with stent-assisted coiling. Although initial occlusion rates are good, the primary limitation of stent-assisted coiling is the inability to provide sustained long-term aneurysm occlusion. Aneurysm recurrence rates of up to 16% have been reported in the literature after stent-assisted coil treatment of small and medium IAs (**Table 2**). The presence of major aneurysm recurrence requires retreatment, which is evidenced by aneurysm retreatment rates of up to 10% for small and medium IAs. Therefore, an alternative approach for obtaining sustained aneurysm occlusion is needed for small and medium wide-necked IAs. Within this current study, the safety and effectiveness of the Pipeline™ device for the treatment of unruptured, wide-necked IAs measuring  $\leq 12$  mm will be investigated.

##### ***IAs in the ICA (Up to the Terminus) and Vertebral Artery Segment (Up to and including the PICA)***

Currently, treatment with the Pipeline™ device is indicated in US for IAs in the ICA from the petrous to the superior hypophyseal segments and the present study aims to include IAs in the ICA up to the terminus. Data from 239 patients with IAs  $\leq 12$  mm located in the ICA up to the terminus were collected in the IntrePED retrospective study which demonstrate neurological

morbidity and mortality rates of 4.2% and 1.7%, respectively (**Table 3**). These rates demonstrate that the Pipeline™ device can serve as a potentially safe treatment option for IAs of the ICA (up to the terminus).

The treatment of IAs in the posterior circulation is typically associated with a higher rate of complications. However when limited to only the vertebral and posterior inferior cerebellar arteries, published literature indicates that the morbidity and mortality rates are similar to the rates reported for stent-assisted coil treatment of small-wide-necked IAs. Studies evaluating the treatment of aneurysms located in the VA or PICA demonstrate morbidity rates ranging 0%-13% and mortality rates ranging 0%-7%. (**Table 4**) These rates are comparable to the stent-assisted coiling morbidity rates of 3.9%-9.2% and mortality rates of 0%-6.8% presented in **Table 1**. Within this current study, the safety and effectiveness of the Pipeline™ device for the treatment of unruptured, wide-necked IAs measuring  $\leq 12$  mm in the vertebral artery segment up to and including the PICA will be investigated.

**Table 4. Morbidity and Mortality Rates of PICA and VA IAs Treated Surgically and Endovascularly**

Article	PICA or VA	Ruptured Prior to Treatment	Morbidity	Mortality
Mukonoweshuro 2003	All PICA	23/23 (100%)	3/23 (13%)	0/23 (0%)
Bradac 2004	All PICA	17/18 (94%)	1/18 (5.6%)	1/18 (5.6%)
Mericle 2006	All PICA	26/31 (84%)	--	2/31 (6.5%)
Pandey 2007	VA and PICA	23/41 (56%)	4/41 (9.8%)	1/41 (2.4%)
Peluso 2008	All PICA	10/47an. (21%)	2/46 (4.3%)	2/46 (4.3%)
Deng 2011	All VA	17/38 (45%)	0/38 (0%)	0/38 (0%)
Crowley 2012	All PICA	13/20 (65%)	2/20 (10%)	0/20 (0%)
Chalouhi 2013	All PICA	61/76 (80%)	2/71 (2.8%)	2/57 (3.5%)

\*All percentages noted are per subject, except where noted.

### **Study Design**

The proposed study design is a single-arm study of unruptured, wide-necked IAs, measuring  $\leq 12$  mm in which subjects will be treated with the Pipeline™ device. Alternative minimally invasive treatments that could form a reasonable concurrent control group are not available. Currently, the most common treatment method for these IAs is stent-assisted coiling. Although stent-assisted coiling is commonly performed, it is also important to note that not all IAs (e.g. fusiform IAs), which can be treated with the Pipeline™ device can be treated with stent-assisted coiling. As a result, if stent-assisted coiling were considered as a control treatment in the proposed study, it would limit the types of aneurysms that could be evaluated in the trial.

As discussed above, the aneurysm retreatment and recurrence rates associated with stent-assisted coiling demonstrate the need for a more durable treatment. In the scenario of a randomized controlled trial, if a subject is randomized to stent-assisted coiling and the IA recurs or enlarges to the extent of requiring retreatment, potential retreatment options will be limited. In particular, retreatment with flow diversion therapy is not possible in cases where a stent is already placed in the target IA. The labeling of the Pipeline™ device specifically states that it is contraindicated in patients who have a pre-existing stent in place in the parent artery at the target IA location.

Furthermore, stents are not approved by the FDA for use in the treatment of IAs and may only be used under the conditions of HDE approval. To date, no endovascular technology with FDA-accepted evidence of effectiveness is commercially available to address small and medium wide-necked IAs.

However, the safety and effectiveness rates associated with stent-assisted coiling for these IAs are published in the literature and can be used to define objective performance criteria. Clinical trial data and published studies have shown that the Pipeline™ device is safe and effective at treating larger sized IAs and it is expected that the Pipeline™ device will perform similarly in smaller IAs. To put the study results into perspective, results will be compared with historical information derived from earlier studies in which subjects with similar IAs underwent stent-assisted coil embolization.

### ***Conclusion***

In summary, IAs can potentially rupture and lead to serious complications with significantly poor outcomes. SAH resulting from aneurysmal rupture is associated with a high mortality rate of 51%. The majority of IAs identified in routine practice are  $\leq 12$  mm in size and the average size of ruptured IAs is approximately 6.6-6.8 mm. Small and medium wide-necked IAs are most commonly treated endovascularly with stent-assisted coiling, however, treatment outcomes are sub-optimal. Given the high recanalization and retreatment rates reported with stent-assisted coiling, alternative options with sustained curative effects are necessary. Treatment with the Pipeline™ device has demonstrated high rates of long term complete occlusion, low rates of retreatment and low rates of adverse transient and persistent neurologic events in large and giant wide-necked IAs. Data collected in the IntrePED retrospective study and published literature suggests that the Pipeline™ device could be a possible treatment option for small and medium wide-necked IAs.

Thus, the aim of the present study is to assess the safety and effectiveness of the Pipeline™ device beyond the present indication to include IAs measuring  $\leq 12$  mm in the ICA (up to the terminus) and vertebral artery segment up to and including the PICA.

## **2 DEVICE DESCRIPTION**

### **2.1 Intended Use of Device**

The Pipeline™ device is intended for endovascular treatment of unruptured, wide-necked IAs, measuring  $\leq 12$  mm, located in the internal carotid artery (up to the terminus) or the vertebral artery segment up to and including the PICA.

The Pipeline™ device (manufactured by Covidien) is a braided, platinum and nickel-cobalt chromium alloy, wire mesh cylindrical implanted device that is intended to treat IAs.

The Pipeline™ device is designed to be placed across the opening (or 'neck') of a brain aneurysm and redirect blood flow away from the aneurysm, causing the blood within the aneurysm to clot. The device is designed for use in the neurovasculature.

### 2.1.1 Device Name

The Pipeline™ device will be used in this clinical study. The implanted braid, shown in **Figure 1**, is mounted on a guidewire-based delivery system.

**Figure 1. Pipeline™ Device Braid**

Continued development on the delivery system is ongoing and Pipeline™ devices with modified delivery systems with no changes to the braid implant may be used in this study upon agreement and approval by FDA.

### 2.2 Device Labeling

The Pipeline™ device is an approved, commercially available device. However due to the modification in indication, the device is considered investigational in this study and is required to be used per the protocol and as specified in the IDE Instructions for Use (IFU) document. The IDE IFU is provided separately to each investigator.

### 2.3 Device Tracking

The Pipeline™ device is tracked by lot number. Usage of all Pipeline™ devices in enrolled subjects who undergo the procedure will be tracked. Due to commercially availability, all shipments will not be tracked for the study.

### 2.4 Devices and Equipment

In addition to the Pipeline™ device, devices that may be required for the study procedure include (but are not limited to) those listed below. All ancillary devices required to perform the procedure will be provided by the site.

- Access devices: Guiding catheter and sheath
- Delivery catheters: Microcatheters (Covidien Marksman is recommended for use with the Pipeline™ device)
- Non-ionic contrast
- Guidewires
- Any other adjunctive, approved/cleared device for intracranial aneurysm treatment

The placement procedure is described in detail in the Instructions For Use (IFU) document.

**Note:** The Investigator should review and understand the complete IDE IFU prior to performing any Pipeline™ device placement in this clinical study.

### 3 STUDY OBJECTIVES

#### 3.1 Primary Endpoints

- Safety: Occurrence of major stroke in the territory supplied by the treated artery or neurological death at 1 year post-procedure
- Effectiveness: Complete aneurysm occlusion (defined by scale of Roy) without significant parent artery stenosis ( $\leq 50\%$ ) at 1 year post-procedure

For the purposes of this study protocol, stroke is defined as a focal neurological deficit of presumed vascular origin persisting more than 24 hours from symptom onset AND a neuro-imaging study or other quantitative study that does not indicate a different etiology. The 24-hour criterion is excluded if the subject undergoes cerebrovascular surgery or dies during the first 24 hours of symptom onset.

The definition includes:

- Subjects presenting with clinical signs and symptoms suggestive of subarachnoid hemorrhage, intracerebral hemorrhage, or cerebral infarction.
- Sudden loss or worsening of visual acuity due to retinal artery occlusion or retinal emboli.

The definition excludes:

- Slowly progressive cranial nerve palsies or progressive visual field deficits due to continued aneurysm growth.
- Stroke events in cases of blood disorders such as leukemia or external events such as trauma.

Stroke severity will be graded by the Investigator as major or minor:

- Major Stroke: A stroke, which is present after seven days and increases the National Institutes of Health Stroke Scale (NIHSS) of the subject by  $\geq 4$ .
- Minor Stroke: A stroke, which resolves completely within seven days OR increases the NIHSS of the subject by  $\leq 3$ .

Neurological death is any subject death due to neurologic reasons.

The safety endpoint events will be adjudicated by an independent clinical events committee (CEC) ([Section 8.1](#)). The effectiveness endpoint will be assessed by an imaging core lab according to the scale of Roy ([Section 8.2.2](#)).

#### 3.2 Secondary Endpoints

- Safety
  - Occurrence of major stroke in the territory supplied by the treated artery or neurological death at 30 days post-procedure due to procedural complications
  - Delayed intracerebral hemorrhage  $>30$  days post-procedure
- Effectiveness: Device deployment success rate at the target site

### 3.3 Additional Data

- Device-related neurologic adverse event rate by 1 year post-procedure
- Modified Rankin Scale (mRS) score at 1 year.
- Aneurysm occlusion at 3 years post-procedure
- Recurrence and retreatment rates at 1, 2 and 3 years post-procedure
- Procedure time
- Radiation exposure (dosage and time)
- Number of Pipeline™ devices utilized

Event-relatedness will be adjudicated by an independent CEC (**Section 8.1**).

The mRS, a validated scoring system for neurologic status after stroke, will be judged by the Investigator and/or staff.

Aneurysm occlusion status will be assessed by an imaging core lab according to the scale of Roy.

## 4 STUDY DESIGN

The study is a global, prospective, single-arm, multi-center clinical study evaluating outcomes in subjects with intracranial aneurysms measuring  $\leq 12$  mm who are treated with Pipeline™ device.

### 4.1 Number of Sites and Subjects

Up to 200 subjects will be enrolled at up to 28 sites worldwide over a period of approximately 18 months to ensure the study has an adequate number of treated subjects; up to 141 (see **Section 9.2**). The enrollment number takes into account an approximate 30% screen failure rate observed in the initial roll-out of the PREMIER study. Each participating investigational site will be allowed to enroll a maximum of 25 subjects who meet all study eligibility criteria (see **Section 4.3**) and are treated with the Pipeline™ device.

### 4.2 Expected Duration of the Study and Subject Participation

Up to 141 subjects who meet the eligibility criteria (see **Section 4.3**) and are treated with the Pipeline™ device will actively participate for up to 3 years. Study participation includes consent, initial screening and baseline, treatment using the Pipeline™ device, discharge exam and follow-up visits at 30 days, 180 days, 1 year, 2 years, and 3 years.

The total study duration is expected to be approximately 54 months.

### 4.3 Study Population

The study population will consist of subjects who have an intracranial aneurysm. Treatment of more than one aneurysm may be permitted, but will require Sponsor approval before the subject can be treated in the study.

#### 4.3.1 Inclusion Criteria

Subjects must meet all of the following general inclusion criteria:

1. Subject has provided written informed consent using the IRB/EC-approved consent form and agrees to comply with protocol requirements.
2. Age 22-80 years.
3. Subject has a target intracranial aneurysm (IA) located in the:
  - a. Internal carotid artery (up to the carotid terminus) OR
  - b. Vertebral artery segment up to and including the posterior inferior cerebellar artery
4. Subject has a target IA that is  $\leq$  12 mm.
5. Subject has a target IA that has a parent vessel with diameter 1.5–5.0 mm distal/proximal to the target IA.
6. Subject has a target IA with an aneurysm neck  $\geq$  4mm or a dome to neck ratio  $\leq$  1.5.
7. Subject has a pre-procedure PRU value between 60–200.

#### **4.3.2 Exclusion Criteria**

The subject must not meet any of the following general exclusion criteria:

[figure not shown]
1. Subject has received an intracranial implant (e.g. coils) in the area of the target IA within the past 12 weeks.
2. Subarachnoid hemorrhage in the past 30 days.
3. Subject with anatomy not appropriate for endovascular treatment due to severe intracranial vessel tortuosity or stenosis determined from baseline or pre-procedure imaging, or a history of intracranial vasospasm not responsive to medical therapy.
4. Major surgery in the last 30 days.
5. History of irreversible bleeding disorder and/or subject presents with signs of active bleeding.
6. Any known contraindication to treatment with the Pipeline™ device, including:
  - a. Stent is in place in the parent artery at the target IA location
  - b. Contraindication to dual antiplatelet therapy
  - c. Relative contraindication to angiography (e.g., serum creatinine  $>2.5$  mg/dL, allergy to contrast that cannot be medically controlled).
  - d. Known severe allergy to platinum or cobalt/chromium alloys.
  - e. Evidence of active infection at the time of treatment (e.g., fever with temperature  $>38^{\circ}\text{C}$  and/or WBC  $>1.5 \cdot 10^9/\text{L}$ ).
7. The Investigator determines that the health of the subject or the validity of the study outcomes (e.g., high risk of neurologic events, worsening of clinical condition in the last 30 days) may be compromised by the subject's enrollment.
8. Pregnant or breast-feeding women or women who wish to become pregnant during the length of study participation.
9. Participating in another clinical trial during the follow-up period that could confound the treatment or outcomes of this investigation.

Before any subject is treated in the study, the baseline angiogram will be reviewed by a Pipeline™ device expert to ensure that the target IA is amenable to treatment with the Pipeline™ device.

## 5 STUDY PROCEDURES

### 5.1 Overview of Study Flow

A representative overview of the study flow is shown below.

### 5.2 Informed Consent and Privacy

A thorough explanation will be provided to the subject (or legally authorized representative) as to the nature and objectives of this study. Details of the study should include (but are not limited to) the following terms:

- Purpose of the study
- Alternative treatments
- Need to return for 30-day, 180-day, 1-year, 2-year, and 3-year follow-up visits
- Participation is voluntary, and there is no penalty for withdrawal
- Potential risks/benefits for participation
- Contact information to ask questions or voice concerns

The study investigator and/or staff are responsible for obtaining written informed consent from each potential subject before any study specific procedures required by the protocol are performed. Informed consent should be obtained in written format and using a form approved by the local IRB/EC. The form should contain standard language consistent with local policies for ensuring privacy of confidential information. All subjects must sign the informed consent prior to any procedures/tests that go beyond initial assessments associated with the standard care for subjects with intracranial aneurysms and before any study related treatment assessments are administered and subject-related health information can be entered into the study database.

***Subjects are considered enrolled in the study once the subject signs the study Informed Consent Form.***

It is the responsibility of the Investigator to give each subject (or subject's legally authorized representative) prior to inclusion in the study, full and adequate verbal and written information regarding the objective of this study and the confidentiality of the data collected.

### **5.3 Screening and Baseline Evaluations**

Each subject will undergo a neurologic examination and assessment using the mRS and NIHSS, blood draw for hematocrit, platelet count, platelet function testing as per standard patient care (e.g. using VerifyNow (Accumetrics)), serum creatinine, and a pregnancy test (if applicable) within 60 days from the planned procedure. In female subjects, pregnancy may be ruled out by urine or blood pregnancy test, or medical history (menopause or surgical sterility). Each subject's relevant medical history and pre-existing conditions will be assessed and documented for all enrolled subjects. Current medication use within the last 30 days will be assessed and documented at baseline.

Subject eligibility assessment is to be performed based on data available to the investigator at the time of screening. This initial screening phase may include review of existing subject information (previously performed angiography, radiographs, laboratory studies, medical history, physical examination, etc.) and referral to the treating physician. Subjects must comply with all inclusion and exclusion criteria. Waivers will not be granted by the sponsor regarding subject inclusion/exclusion criteria.

If the subject meets the dimensional criteria outlined in the inclusion criteria, they should be included on the study screening log. The reason of non-eligibility for all subjects who are deemed ineligible by the Investigator should also be recorded on the study screening log. The screening log serves as a method for Covidien to ensure that there is no selection bias in the trial.

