### **5.4 Procedure**

Subjects must undergo the device placement procedure within 60 calendar days of completion of all baseline assessment tests and procedures. The status of the target IA may change between the screening evaluation and the procedure that may change the risk profile of the study procedure.

Therefore, a pre-treatment (baseline) angiogram will be required before the procedure to confirm that the study procedure can be safely carried out and to collect precise images for the core laboratory. If in the unlikely event that the subject is deemed to be ineligible, the subject will not require any study follow-up.

Each subject will undergo a neurologic examination and assessment using NIHSS. The subject will be tested for antiplatelet response (e.g. using VerifyNow (Accumetrics)). Periprocedural heparin per institutional protocol is required. Prior to inserting the study device, the activated clotting time (ACT) should be checked and adjusted as clinically appropriate. Further ACTs will be checked per standard practice.

The physician will place and deploy the appropriate number of Pipeline™ device braids at the target site to treat the IA.

Post-treatment, the investigator will assess device occlusion, placement and overall status of the aneurysm. Angiograms in the anteroposterior (AP), lateral, and working positions will be obtained. The Investigator will take necessary steps to ensure that pre- and post-placement angiograms are performed using similar views, magnifications, and contrast amount to ensure valid “before/after” comparisons. However, these angiographic details will not be collected in case report forms (CRFs). The Investigator will submit procedural angiograms to the imaging core laboratory. The Investigator will ensure that subject identifiers are removed from all submitted images. Image files/CDs should be labeled with the subject’s study ID number.

Medications appropriate for general anesthesia will be administered using standard hospital practice. Platelet inhibition and aggregations status pre- and post-surgical intervention, including antiplatelet antibodies will be evaluated. All medication use during surgery and immediately post-procedure will be documented. Radiation exposure will be recorded as absorbed radiation dose and cumulative fluoroscopy time will be recorded.

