## 5.8 Schedule of Assessments

An overview of the assessments to be performed at each follow-up interval along with the required timing is provided in **Table 5**. Visits occurring outside of the specified date range will be considered protocol deviations.

Visits		Screening and Baseline	Device placement		Follow-up					
Assessments	Time (Windows)	Pre-procedure (-60days)	Procedure	Discharge exam	30-day	180-day	1-year	2-year	3-year	Unscheduled
Assess Inclusion / Exclusion		◆								
Demographics and Medical History		◆								
Blood Labs		◆ 	◆ 	○ 						
Medications		◆	◆	◆	◆	◆	◆	◆	◆	◆
Modified Rankin Scale score		◆		◆	◆	◆	◆	◆	◆	
Imaging 	(180 days)	◆ 			○ 	◆	◆ 	◆ 	◆ 	
NIH Stroke Scale		◆	◆	◆	◆	◆	◆	◆	◆	◆
Pipeline™ Placement			◆							
Assess Adverse Events		◆	◆	◆	◆	◆	◆	◆	◆	

1 Includes CBC, HCT, platelet count, platelet function testing as per standard patient care, serum creatinine, and pregnancy test, if applicable

2 Includes platelet count and platelet function testing

3 If platelet function testing is performed as standard patient care the results should be recorded.

4 Includes angiograms in the anteroposterior, lateral and working positions for analysis by a core laboratory.

5 Includes a pre-treatment and post-treatment angiogram

6 If an angiogram is performed as standard patient care it should be sent to the core laboratory for analysis.

7 If aneurysm is completely occluded at 1 year, angiography is optional at subsequent follow-up visits. Otherwise if aneurysm is not occluded at 1 year, angiography must be performed thereafter until the aneurysm is completely occluded or the subject has completed the study.

Any angiograms performed at other time points should be sent to the core laboratory for analysis.

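### The only scheduled pregnancy test can be up to 60 days old at implant and is not repeated on the procedure day

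*Combined protocol and SAP*

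**What the plan says.** **Screening.** Section 5.3 lists the baseline bloods and ends the list with "serum creatinine, and a pregnancy test (if applicable) within 60 days from the planned procedure". It accepts a urine or blood test, or a history of menopause or surgical sterility. It also bases the eligibility assessment on what the investigator knows at screening, and it allows no waivers.

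**Interval to implant.** Section 5.4 sets the same limit from the other side: "Subjects must undergo the device placement procedure within 60 calendar days of completion of all baseline assessment tests and procedures".

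**Procedure day.** In Table 5 (Section 5.8) the pregnancy test appears only in footnote 1, with the screening bloods. Footnote 2, for the procedure day, reads "Includes platelet count and platelet function testing". The synopsis schedule agrees. The inclusion/exclusion row is marked once, at screening and baseline.

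**Exclusions.** Section 4.3.2, item 8, excludes "Pregnant or breast-feeding women or women who wish to become pregnant during the length of study participation". Item 4 reads "Major surgery in the last 30 days" and does not say which date the 30 days precede.

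**The concern.** The plan bars pregnant women but tests for pregnancy only once, at a point that may lie two months before treatment. A conception after that test, or too shortly before it to turn the test positive, can pass every scheduled step. The protocol already draws blood on the procedure day, but not for the test on which exclusion 8 depends.

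The exposures are set by the protocol itself. Sections 5.3.2 and 5.5 require aspirin and clopidogrel for at least 7 days before implant, then clopidogrel for at least 3 months and aspirin for at least 6. Section 5.4 provides for fluoroscopy and general anesthesia, and states: "Periprocedural heparin per institutional protocol is required".

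A lesser matter is exclusion 4. If its 30 days are counted from screening, a subject who has elective major surgery between screening and Day 0 could receive dual antiplatelet therapy and heparin soon after that operation. That is the hazard the criterion appears meant to avoid.

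**Working it through.** **1. Age of the test at implant.** The plan's figure is a maximum of 60 days, stated in both 5.3 and 5.4. Footnotes 1 and 2 of Table 5 show no later test, so the test can be 60 days old on Day 0. Section 5.4 also lets a subject who was not treated at the first scheduled procedure return later, with the implant date becoming Day 0. It does not say that the baseline tests are repeated then. Read strictly, the 60-day limit still applies, so 60 days is the figure used here.

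**2. Expected number.** From the documents: 141 treated subjects (Section 9.2) and the 60-day maximum. Assumed, because the documents do not give them:
- share of treated subjects who are women able to conceive: 10% to 30% (14 to 42 of 141)
- proportion of them conceiving per year: 1% to 9%
- detection lag of a test: 14 days

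Expected conceptions not caught by testing at implant = 141 × share × annual rate × (gap + 14)/365. With a procedure-day test the gap is 0, so 14 days remain.

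| Gap | Low: share 0.10, rate 0.01 | High: share 0.30, rate 0.09 |
|---|---|---|
| 60 days | 141 × 0.10 × 0.01 × 74/365 = 0.029 | 141 × 0.30 × 0.09 × 74/365 = 0.772 |
| 30 days | 141 × 0.10 × 0.01 × 44/365 = 0.017 | 141 × 0.30 × 0.09 × 44/365 = 0.459 |
| Day-0 test | 141 × 0.10 × 0.01 × 14/365 = 0.005 | 141 × 0.30 × 0.09 × 14/365 = 0.146 |

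The reduction is 60/74 = 81% at a 60-day gap and 30/44 = 68% at a 30-day gap. The remainder is 14/74 = 19% and 14/44 = 32%. These percentages depend only on the gap and the assumed 14 days.

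**3. Exclusion 4.** A 30-day look-back counted from screening and one counted from Day 0 share max(0, 30 − gap) days: 23 at a gap of 7 days, 15 at 15 days, and 0 from 30 days onward. At longer gaps the two readings cover entirely different periods. This is calendar arithmetic and says nothing about how often surgery occurs in the interval.

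**The case against.** **Procedure-day checks already exist.** Section 5.4 requires a pre-treatment angiogram, a neurologic examination with NIHSS and antiplatelet-response testing. It provides for a subject found ineligible at that point. Table 5 adds adverse event and medication review. A reader might infer that all the look-back exclusions go unchecked, including item 1 ("Subject has received an intracranial implant (e.g. coils) in the area of the target IA within the past 12 weeks") and item 2 ("Subarachnoid hemorrhage in the past 30 days"). The documents do not support that. A new implant at the target would probably be seen on the angiogram. An interval hemorrhage is a neurological adverse event, collected from consent onward under Section 6. None of these steps detects a pregnancy, however, and pregnancy as such is in none of the four adverse event categories in Section 6. Elective surgery can also be missed, because Section 6.1 does not count a planned admission for a pre-existing condition as a serious adverse event.

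**The reference date is implied.** Section 5.3 points to screening as the time at which eligibility is judged. That is fair, so naming a date is mainly a matter of detail. It still leaves the interval to implant open for exclusion 4.

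**The counts are soft.** This stands. Share, rate and detection lag are all assumed, and the 60-day row puts every subject at the permitted maximum. The formula counts all conceptions, including those a woman already knows of, and exclusion 8 bars her without a test. The figures are therefore ceilings on unrecognized pregnancies, given the inputs, and not forecasts.

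**The fix is partial.** A reader might infer that one test makes every case avoidable. The residual of 0.005 to 0.15 shows otherwise. A Day-0 test also comes after at least 7 days of aspirin and clopidogrel.

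**Contraception and hospital policy.** The lack of a contraception requirement in the text available should carry no weight, because the consent pages were removed and the IDE instructions for use are a separate document. Hospitals may test under their own policy, but the protocol does not require it of its up to 28 sites.

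**Conclusion.** The pregnancy point holds. As written, the plan permits implant on a pregnancy test up to 60 days old with no repeat, so exclusion 8 is not verified when treatment is given. It is a low-severity participant-safety point: the expected number of cases is below one across the whole assumed range. The conclusion about the text does not rest on those assumptions; only the size does. The documents give neither the distribution of screening-to-implant gaps nor the number of women able to conceive.

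Of the look-backs, only exclusion 4 is clearly left without a procedure-day check, and that is a secondary wording matter. Nothing here bears on sample size, type I error or power, and no effect on the primary results is claimed.

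**What to change.** **Main change.** In Section 5.4 and Table 5, require a repeat urine or blood pregnancy test on the procedure day, before anesthesia and fluoroscopy, for women in whom pregnancy is not ruled out by menopause or surgical sterility. State that this applies equally to a rescheduled Day 0. Update the synopsis schedule to match.

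**Secondary change.** In Section 4.3.2, state that the 30 days in exclusion 4 count back from Day 0, and add a one-line confirmation to the procedure form.

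**Cost.** One rapid test for the women concerned, one form item, a few words of protocol text, and an occasional subject excluded on the day. The gain is to prevent most exposures to anesthesia, fluoroscopy, heparin, the implant and continued antiplatelet therapy in an unrecognized pregnancy.
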